### **3.3 Total Number of Study Sites/Total Number of Subjects Projected**

#### **3.3.1 Duration of Study Participation**

##### **3.3.1.1 Subjects with OSAS**

The study duration is estimated at 12-14 months approximately. However, this will depend on the timing of treatment as they will undergo testing pre- and post-OSAS treatment. Their participation will entail a total of 8 visits:

Pre-treatment: The cognitive and behavioral, and CBF during wakefulness testing duration is one full day. The CBF nighttime testing is one full night.

Post-treatment: Six to twelve weeks after clinically indicated surgical treatment, OSAS participants will have a repeat baseline polysomnogram (one full night) to assess for residual OSA. Six and twelve months after the surgical treatment, the sleep study with the nighttime CBF testing, as well as the daytime neurobehavioral and CBF testing will be repeated to assess for changes.

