#### 4.1.2 Visit 2: Daytime, 1 to 30 days after screening visit

- Mallampati airway score and tonsillar assessment
- Cognitive and behavioral testing
- CBF testing during wakefulness during hypercapneic ventilatory response

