#### 4.1.4 Visit 4: Daytime, 6 months after adenotonsillectomy

- Cognitive and behavioral testing
- CBF testing during wakefulness during hypercapneic ventilatory response

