**4.1.6 Visit 6: Daytime, 12 months after adenotonsillectomy**

- Cognitive and behavioral testing
- CBF testing during wakefulness during hypercapneic ventilatory response

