**4.2.4 Visit 4: Daytime, 6 months after Visit 1**

- Cognitive and behavioral testing
- CBF testing during wakefulness during hypercapneic ventilatory response

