**4.2.5 Visit 5: Nighttime, 6 months after Visit 2**

- Height/weight assessment
- CBF testing during sleep during hypercapnic ventilatory response

---

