#### 6.4.2 Analysis of Primary Outcome of Interest

The primary analysis will include all subjects meeting all inclusion and exclusion criteria and completing all study visits.

The primary endpoint will be the change in CBF in OSAS and controls at baseline.

The secondary endpoint will be the change in CBF in OSAS and controls at 6 and 12 months after baseline measurements for controls and after adenotonsillectomy for OSAS.

Longitudinal models using generalized estimating equations (GEE) will be fitted to explore effects of treatment on CBF and NBT. An indicator variable for treatment, time, and a time by treatment group interaction term will be included in the models. If the interaction term

---

differs significantly from zero, this will indicate that the change over time in the outcome of interest differs significantly between the two groups. We will assess the sensitivity of results to the choice of working correlation structure that models association in the GEE analyses. We will also implement quasi-least squares (QLS), an approach based on GEE that allows for implementation of the Markov correlation structure.(32) The Markov structure is plausible if participants have unequal temporal spacing of their measurements. In addition, we will consider the application of mixed effects models if the assumptions of these models are met. An indicator variable for subjects who resolve after treatment versus those who do not resolve after treatment will be included in the model to account for those children whose OSAS may not resolve after surgery.(22, 33, 34) Pre-, post treatment change in AHI will be included in the model, and potential confounding variables such as age, gender, race, socio-economic status and BMI will also be included in the models.

Hypercapnic ventilatory responses will be controlled for BMI as obese participants may have different responses compared to non-obese participants.

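### Follow-up is timed from surgery in OSAS children but from the first or second visit in controls, so the secondary longitudinal comparison spans unequal intervals, with a time variable that is never defined

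*Combined protocol and SAP*

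**What the plan says.** Section 6.4.2 makes the baseline group comparison of CBF change the primary endpoint. The secondary endpoint is CBF change "at 6 and 12 months after baseline measurements for controls and after adenotonsillectomy for OSAS". GEE models with group, time and their interaction are fitted, and a non-zero interaction is read as a difference between groups in change over time. The section does not say whether time means nominal visit, months since baseline or months since surgery. It mentions unequal spacing only as a reason to consider a Markov working correlation. Age is a listed covariate, without saying whether it is age at entry or at each test.

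For OSAS children, the daytime baseline tests are at "Visit 2: Daytime, 1 to 30 days after screening visit" (4.1.2), before surgery. Follow-up is at "Visit 4: Daytime, 6 months after adenotonsillectomy" (4.1.4) and "Visit 6: Daytime, 12 months after adenotonsillectomy" (4.1.6), with night visits on the same surgical clock. Section 3.3.1.1 estimates 12-14 months of participation but adds that "this will depend on the timing of treatment as they will undergo testing pre- and post-OSAS treatment". No limit on the interval from baseline to surgery is given.

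For controls, Visit 1 is screening, without CBF or cognitive tests (4.2.1, Table 2). The baseline tests are at Visit 2 (day) and Visit 3 (night), each 1-30 days after screening. Section 4.2.4 reads "Visit 4: Daytime, 6 months after Visit 1", and Visits 6 and 7 also count from Visit 1. Section 4.2.5 instead reads "Visit 5: Nighttime, 6 months after Visit 2".

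**The concern.** The synopsis rationale gives the purpose of retesting everyone over about a year: to tell changes due to OSAS treatment from changes due to development. That works only if controls are observed over the same span as OSAS children, or if the model allows for the difference. Here the OSAS span is 6 or 12 months plus the wait for surgery, while the control daytime span is 6 or 12 months less the lag from Visit 1 to Visit 2. Both departures lengthen the OSAS interval relative to the control interval.

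A Markov structure changes how strongly visits are taken to correlate. It does not change the fitted mean. If the mean model treats both groups' second measurement as 6 months, part of any maturation in OSAS children is credited to treatment. For daytime tests the discrepancy has the same sign in every comparison, so a larger sample would not remove it.

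**Working it through.** **The plan's own figure.** Section 6.5 gives 50 per group, effect size 0.566, two-sided 0.05 and 80% power. The noncentral t calculation gives 80.0%, and 50/(1 - 20/70) = 70 matches the recruitment target. Both reproduce. They concern a two-group t-test, not the interaction.

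**Intervals.** Let L be the lag from Visit 1 to the baseline test (1-30 days, or 0.03-0.99 months at 30.44 days per month), g the wait from OSAS Visit 2 to surgery, and P the total OSAS participation in months.

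- Control, day: 6 - L and 12 - L, that is 5.01-5.97 and 11.01-11.97 months.
- OSAS, day: 6 + g and 12 + g.
- Daytime excess in OSAS: g + L(control).
- Since P = L(OSAS) + g + 12, the excess equals (P - 12) + L(control) - L(OSAS).
- With P = 12-14 and similar lags in the two groups, the excess is 0-2 months. With a 1-day OSAS lag and a 30-day control lag, the upper end is 2 + 0.95, about 3 months.
- Control, night, 12 months: Visit 3 to Visit 7 is 11.01-11.97 months. If the OSAS night baseline is at the combined screening visit and Visit 1 (4.1.1), the OSAS interval is P, so the excess is (P - 12) + L, up to about 3 months.
- Control, night, 6 months: Visit 5 runs from Visit 2 and the baseline is Visit 3, so the interval is 6 + L(Visit 2) - L(Visit 3), or 5.05-6.95 months. The excess can then be small or, with a very short wait, negative. Hence generally longer, not always longer.

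**Bias.** Assume equal linear drift in both groups of 0.25-0.5 SD per year (SD between children at one visit), nominal visit coding, 50 per group, and correlation r = 0.5-0.7 between visits. None of the drift or correlation values is in the documents.

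- Bias = drift x excess/12.
- SE of the difference in change = sqrt(2 x 2(1 - r)/50): 0.200 at r = 0.5 and 0.155 at r = 0.7.
- Rejection rate with no treatment effect = Φ(-1.96 - bias/SE) + Φ(-1.96 + bias/SE).

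| Excess (months) | Drift (SD/year) | Bias (SD) | Rejection, r = 0.5 | Rejection, r = 0.7 |
|---|---|---|---|---|
| 0 | any | 0 | 5.0% | 5.0% |
| 1 | 0.25 | 0.021 | 5.1% | 5.2% |
| 1 | 0.5 | 0.042 | 5.5% | 5.8% |
| 2 | 0.25 | 0.042 | 5.5% | 5.8% |
| 2 | 0.5 | 0.083 | 7.0% | 8.4% |
| 3 | 0.25 | 0.063 | 6.1% | 6.9% |
| 3 | 0.5 | 0.125 | 9.6% | 12.7% |

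An assumed 6-month wait with a 30-day control lag gives an excess of 6.99 months. At 0.5 SD per year and r = 0.5 the bias is 0.29 SD and the rejection rate about 30% (t-test calculation). The documents do not say that such waits are expected. They also do not rule them out.

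**The case against.** The strongest reply is that the plan never commits to nominal time. A reader might infer from the 6- and 12-month endpoint labels that the GEE uses nominal visits, and that age enters as a baseline covariate. Section 6.4.2 states neither, and its remark on unequal spacing shows that irregular timing was expected. If the analysts use actual months since baseline, or age at each test, much of the bias goes. This stands as a limit: the defect is unequal visit anchors combined with an undefined time variable, not a proven coding error.

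Other stronger readings also fail.

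- That every control interval is 5-6 months at the first follow-up: Section 4.2.5 breaks the pattern for the night visit, and 6.4.2 itself refers to baseline measurements.
- That 12-14 months of participation implies an excess of at least 1 month: with similar lags in both groups it implies 0-2.
- That the artefact must look like benefit from surgery: the documents give no developmental direction for the CBF response to hypercapnia, and drift the other way would hide a benefit.
- That practice effects drive it: both groups have three test sessions, so exposure is equal. Maturation is the relevant mechanism, and age-normed scores would reduce it for some cognitive measures.

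Scope is also limited. The GEE is described as exploring treatment effects, and the treatment endpoints in Section 6.2 are before-after comparisons within OSAS. What remains is that the anchors as written produce unequal spans in the comparison that is meant to separate treatment from development, and nothing in the plan commits the mean model to allowing for this.

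**Conclusion.** The point holds for the secondary longitudinal analysis only. If participation stays within 12-14 months, the distortion is modest: at most about 0.08 SD and 8% false positives at an excess of 2 months, and 0.125 SD and about 13% when the extremes of interval, drift and correlation coincide. It grows with the wait for surgery, which the protocol does not bound. These figures rest on assumed linear drift, equal in both groups, assumed correlations and nominal visit coding. The sign depends on the direction of maturation. A reader might infer that the main result or the sample size is at risk. It is not, because the primary endpoint is the baseline comparison. The conflict among the control anchors needs reconciling whatever the size of the bias. The change is worth making before analysis but is not critical.

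**What to change.** In Section 6.4.2, define time in the mean model as actual months from each child's own baseline CBF or cognitive test, or use age at each test, and add OSAS-specific post-surgery terms at 6 and 12 months. The elapsed-time term then carries maturation and the post-surgery terms carry the treatment contrast. A group-by-months slope alone would not separate them. State the remaining assumption that the two groups mature alike. Keep the Markov structure as a choice about correlation only.

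Reconcile Sections 4.2.4 to 4.2.7 with 6.4.2 so that each control follow-up test is timed from its own baseline visit: daytime from Visit 2, night from Visit 3. This alone does not deal with the wait for surgery, so the model change is the essential part. Neither change touches the timing of surgery.

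The cost is revised SAP wording, slightly more modelling, a small shift in control visit windows and use of each test's date in the analysis. No extra children or procedures are needed.

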### **3.2 Study Duration, Enrollment and Number of Sites**

Duration of study participation for the subject will be 12-14 months approximately.

---

We plan to enroll 70 subjects in each arm in order to have 50 evaluable subjects in each arm at the end of the study. This research will be carried out at one site only: Children's Hospital of Philadelphia.

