#### **3.3.2 Total Number of Study Sites/Total Number of Subjects Projected**

The study will be conducted at one investigative site only: Children's Hospital of Philadelphia.

Recruitment will stop when approximately 140 subjects are enrolled. It is expected that approximately 140 subjects will be enrolled to produce 100 evaluable subjects (50 in each arm).

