## **6.5 Sample Size and Power**

A sample size of 50 in each group (total N = 100) will have 80% power to detect a moderate effect size of 0.566 using a two group t-test with a 0.05 two-sided significance level. We plan to recruit 70 in each group to account for attrition.

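### The 6- and 12-month models state no missing-data assumption and no clear analysis set despite 28.6% planned attrition; a likelihood-based repeated-measures model on all available data should lead

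*Combined protocol and SAP*

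**What the plan says.** **Attrition.** Section 3.2: "We plan to enroll 70 subjects in each arm in order to have 50 evaluable subjects in each arm at the end of the study". Section 6.5 repeats it: "We plan to recruit 70 in each group to account for attrition".

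**Method.** Section 6.4.2: "Longitudinal models using generalized estimating equations (GEE) will be fitted to explore effects of treatment on CBF and NBT". The model has group, time and their interaction, plus covariates. Two additions stay within the same family: "We will assess the sensitivity of results to the choice of working correlation structure that models association in the GEE analyses", and quasi-least squares (QLS) with a Markov correlation. The only likelihood-based method is conditional: "In addition, we will consider the application of mixed effects models if the assumptions of these models are met".

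**Analysis set.** Section 6.4.2 opens by confining the primary analysis to eligible children who attended every study visit. It then places the primary endpoint at baseline and the secondary endpoint at 6 and 12 months. No other set is defined.

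**Not stated anywhere.** A missing-data assumption, weighting, imputation, a missing-data sensitivity analysis, or which working correlation is primary.

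**The concern.** Unweighted GEE is valid in general only when dropout is unrelated to a child's scores. If it depends on scores already observed, the estimate is approximately right only when the working correlation is close to the true one. Comparing working correlations then mixes dropout bias with efficiency, and the plan has no rule for which result to believe. If the models use completers only, the working correlation stops mattering, but the bias from selecting completers takes its place.

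Score-related loss is plausible here, though not shown. Section 4.5 lets the investigator withdraw children who cannot manage the instructions or the tests, which is close to the cognitive and behavioural outcomes. Only OSAS children have surgery and an additional post-operative visit, so loss could differ by group. At stake is the secondary objective in section 2.2, improvement after treatment. Section 6.2 also lists before-and-after change within the OSAS group, where no control arm can offset a bias.

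**Working it through.** **1. Reproduce the plan's figures.** Section 6.5: "A sample size of 50 in each group (total N = 100) will have 80% power to detect a moderate effect size of 0.566". The comparison behind this figure is a two-sided t-test at the 5% level.

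- Sample size by the normal formula: n = 2(1.960 + 0.842)²/0.566² = 49.0, just above 49, so 50 per group.
- Power at n = 50: the standardised difference is 0.566 × √(50/2) = 2.83, and Φ(2.83 − 1.96) = 0.808. The exact noncentral t gives 0.800.
- Attrition: 1 − 50/70 = 0.286, and 50/(1 − 0.286) = 70.

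The stated design is internally correct.

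**2. Bias in the 12-month within-group change.** Large-sample simulation of one group: 400,000 children, three visits, SD 1, true change 0, monotone dropout with about 28.6% lost by 12 months. Assumptions not in the documents: within-child correlation 0.3 to 0.7, exchangeable or AR(1); log-odds of dropout rising by 0.5 or 1.0 per SD of the last observed score (odds × 1.65 or × 2.7). Entries are in SD units.

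| True correlation | Log-odds per SD | Independence GEE | Exchangeable GEE (estimated) | AR(1) GEE | Completers only |
|---|---|---|---|---|---|
| 0.3 exchangeable | 0.5 | −0.042 | +0.002 | −0.013 | +0.055 |
| 0.3 exchangeable | 1.0 | −0.079 | −0.003 | −0.026 | +0.094 |
| 0.3 AR(1) | 0.5 | −0.025 | +0.011 | +0.004 | +0.072 |
| 0.3 AR(1) | 1.0 | −0.055 | +0.005 | −0.002 | +0.118 |
| 0.5 exchangeable | 0.5 | −0.075 | −0.001 | −0.019 | +0.038 |
| 0.5 exchangeable | 1.0 | −0.134 | −0.007 | −0.032 | +0.066 |
| 0.5 AR(1) | 0.5 | −0.055 | +0.008 | +0.001 | +0.057 |
| 0.5 AR(1) | 1.0 | −0.100 | +0.009 | +0.001 | +0.098 |
| 0.7 exchangeable | 0.5 | −0.105 | −0.002 | −0.016 | +0.021 |
| 0.7 exchangeable | 1.0 | −0.182 | −0.007 | −0.025 | +0.040 |
| 0.7 AR(1) | 0.5 | −0.089 | +0.005 | −0.001 | +0.036 |
| 0.7 AR(1) | 1.0 | −0.159 | +0.003 | −0.001 | +0.064 |

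Here higher scorers leave. If lower scorers leave, every sign reverses. Weighting by the true dropout model brought the bias to within 0.005 SD.

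At 6 months the biases are smaller: 0.02 to 0.10 SD for independence and at most 0.006 SD for completers.

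**3. Why the structure is irrelevant for completers.** When every child has all three visits and each visit has its own mean per group, the GEE solution for change is the difference of visit means under any working correlation. The simulation agreed to three decimals under independence, exchangeable and AR(1).

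**4. Other assumptions.** With lower scorers leaving, 300,000 children and correlations up to 0.8, log-odds of 1.0 gave +0.13 to +0.19 SD for independence, about 0.01 SD or less for exchangeable, within 0.005 SD for a likelihood model with the correct covariance, and −0.04 to −0.07 SD for completers. A two-group run with score-related dropout in OSAS only (15,000 per group), measured against the likelihood model, gave +0.12 to +0.19 SD for independence and −0.03 to +0.06 SD for exchangeable.

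**5. From one group to the interaction.** Bias in the difference in change is the OSAS bias minus the control bias. Take the 0.5 exchangeable rows, independence GEE, in absolute size:

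- same mechanism in both groups: 0.134 − 0.134 = 0
- weaker in controls: 0.134 − 0.075 = 0.059
- unrelated to score in controls: 0.134 − 0 = 0.134

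**The case against.** **The completer rule may govern.** If it does, the working correlation is beside the point, and replacing GEE with a mixed model on the same completers would remove nothing. This stands. It is why the analysis set must be settled along with the model. The rule is worded for the primary analysis, whose endpoint is at baseline, so the text supports neither reading firmly.

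**The largest figure belongs to a structure the plan does not name.** Section 6.4.2 names only Markov, through QLS. Exchangeable and AR(1) structures are nearly unbiased here. This stands too. But independence is not ruled out and no structure is primary.

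**The mechanism is assumed.** The documents do not show that loss follows scores. Some of the 20 per group may be unusable optical recordings (section 4.4), discarded rebreathing tests (section 5.1.3) or controls failing the screening sleep study. Dropout explained by the planned covariates would not bias GEE, and the simulations contain no covariates. The sizes are therefore conditional.

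**The models are exploratory and secondary, with several methods listed.** That lowers the weight of the point. It does not supply a missing-data assumption.

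**A stronger inference to avoid.** A reader might divide 0.19 by 0.566, get 0.34, and conclude that dropout could distort the result by a third of the planning effect. The documents do not support this. Section 6.5 sizes a two-group t-test and section 6.4.2 puts the primary comparison at baseline. A 12-month difference in change is another quantity with another SD.

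**Conclusion.** The point holds as a gap in specification that is inexpensive to close. With 28.6% attrition planned, the 6- and 12-month analyses have no missing-data assumption, no primary working correlation and no clear analysis set.

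If dropout depends on earlier scores and differs between groups, the 12-month change is biased on either reading:

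- **All available data:** roughly 0.06 to 0.19 SD under independence when within-child correlation is 0.5 or more (down to about 0.03 SD at 0.3), and a few hundredths of an SD under exchangeable or similar structures.
- **Completers only:** roughly 0.02 to 0.12 SD whatever the structure, with the opposite sign to independence GEE in step 2 of the working.

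These sizes rest on assumed correlations and dropout strength. The documents do not establish that such bias will occur, or that it must depend on the working correlation. The baseline primary comparison is outside this point.

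**What to change.** In section 6.4.2:

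1. State that the 6- and 12-month analyses include all eligible children with at least one measurement, not only those who complete every visit.
2. Make the main longitudinal analysis a likelihood-based repeated-measures model with categorical visit, group-by-visit interaction, unstructured covariance and the planned covariates. State that it assumes data are missing at random.
3. Keep GEE and QLS as sensitivity analyses, without independence working correlation when visits are missing.

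**Cost.** Analysis wording only. Three visits need 3 × 4/2 = 6 covariance parameters, which is feasible with about 140 children. The model relies slightly more on a correct covariance; the unstructured form and the retained GEE analyses limit this. It gives no protection if dropout depends on scores that were never observed.

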**FIGURE 3: CONTROLS STUDY VISIT DIAGRAM**

## 1 BACKGROUND INFORMATION AND RATIONALE

### 1.1 Introduction

The obstructive sleep apnea syndrome (OSAS) is common, affecting 2-3% of children.(1) It is associated with significant morbidity such as growth failure,(2) systemic,(3-5) and pulmonary hypertension, (6, 7) endothelial dysfunction,(8, 9) and cognitive and behavioral impairment.(10) This is important as the brain undergoes crucial development during childhood and thus, the long-term consequences of cognitive and behavioral dysfunction may have great impact in children's future adult life. Imaging studies of adults with OSAS have identified abnormal morphology of the frontal cortex, an important area for executive function.(11, 12) Other studies using magnetic resonance spectroscopy imaging have shown altered central nervous system metabolites of neuronal white and gray matter in adult and children with OSAS, which may be indicative of neuronal injury.(13) Researchers have hypothesized that this neuronal injury results in cognitive and behavioral consequences, and is caused by OSAS-associated hypoxemia. OSAS, however, is not only characterized by periods of hypoxemia. OSAS patients experience hypercapnia and frequent arousals from sleep as well, as a consequence of the repetitive episodes of upper airway obstruction that are the hallmark of OSAS.(14, 15) In fact, we have shown that children with OSAS, during wakefulness, have blunted CBF responses to hypercapnia compared to normal controls. (16) Therefore, the overall aim of this research protocol is to further delineate the mechanisms by which behavioral and cognitive dysfunction occur in children with OSAS based on our previous CBF findings. The overall hypothesis is that children with OSAS have abnormal Cerebral Blood Flow (CBF) regulation during wakefulness and sleep, manifested by blunted CBF response to hypercapnia that improves after treatment of OSAS. We further hypothesize that this CBF dysregulation correlates with the degree of behavioral and cognitive dysfunction.

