### **2.2 Secondary Objectives (or Aim)**

To determine whether this cerebral blood flow regulation impairment, and cognitive and behavioral measurements improve after treatment of OSAS.

Other secondary objectives are to determine the association between:

- Cerebral blood flow regulation and severity of OSAS.
- Cognitive and behavioral measurements and severity of OSAS.

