#### 4.1.3 Visit 3: Post-Operative sleep study 6-12 weeks after adenotonsillectomy

- Sleep study to assess resolution of OSAS. If the post-operative AHI is  $\geq 5$  events per hour, participants will be referred to clinical care. However, they will continue in the study and perform procedures as planned. Data collected from such participants will be analyzed separately.
- Height and weight assessment.

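### The treatment-effect GEE in section 6.4.2 includes two results of surgery with no stated coding, so its time-by-group term has no fixed meaning

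*Combined protocol and SAP*

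**What the plan says.** Section 6.4.2 (Analysis of Primary Outcome of Interest) fits GEE models for CBF and neurobehavioral outcomes with group, time and their interaction. Of an interaction that differs from zero it says that "this will indicate that the change over time in the outcome of interest differs significantly between the two groups".

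The same paragraph then adds two quantities known only after surgery:

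- Resolution: "An indicator variable for subjects who resolve after treatment versus those who do not resolve after treatment will be included in the model". The stated purpose is "to account for those children whose OSAS may not resolve after surgery".
- AHI: "Pre-, post treatment change in AHI will be included in the model".

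For neither term does it give the value in controls, the value at the baseline visit, the reference level, any interaction with time, or a definition of resolution. No model without the two terms is named.

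Section 4.1.3 describes Visit 3, 6-12 weeks after surgery, as a "Sleep study to assess resolution of OSAS". Of children whose AHI is then 5 per hour or more it says: "Data collected from such participants will be analyzed separately". Section 6.4.2 instead keeps unresolved children in the pooled model with an indicator, and does not tie its notion of resolution to that cut-off.

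The model serves the secondary objective in section 2.2: "To determine whether this cerebral blood flow regulation impairment, and cognitive and behavioral measurements improve after treatment of OSAS".

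**The concern.** Age, gender, race, socio-economic status and BMI are listed in 6.4.2 as potential confounders. AHI change and resolution are different in kind: they are what surgery produces. Section 1.1 hypothesises a "blunted CBF response to hypercapnia that improves after treatment of OSAS". If that improvement comes about by relieving obstruction, both terms lie on the path from treatment to outcome, and holding them fixed over time removes part or all of the effect being tested.

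Whether this happens depends on a coding that the plan leaves open. Two analysts who both follow 6.4.2 could report different quantities under one label, and the choice could be made after the results are seen. It will matter in practice, because sections 1.2 and 6.4.2 both expect some children not to resolve after surgery.

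**Working it through.** **The plan's own figure.** Section 6.5 states 80% power with 50 per group, effect size 0.566 and two-sided alpha 0.05. The noncentrality is 0.566 × √(50/2) = 2.83. The noncentral t distribution gives 80.0% (n = 49.98 per group). The figure reproduces. It belongs to a two-group t-test, not to the GEE, so nothing below changes it.

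**What the interaction means under each coding.** Let G = 1 for OSAS, P = 1 after baseline, R = 1 if resolved. Write the mean as b0 + b1·G + b2·P + b3·G·P plus the extra term. To isolate the coding, suppose resolved and unresolved children start at the same level.

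- Extra term c·R (child-level main effect). Every OSAS child changes by b2 + b3 whatever R is, and controls by b2. So b3 is the total contrast, but R cannot make unresolved children's change differ. With an identity link, complete data, and the same visit times and working correlation for every child, the estimate of b3 is exactly unchanged.
- Extra term c·R·P, controls 0. Unresolved children change by b2 + b3, resolved by b2 + b3 + c, controls by b2. So b3 is unresolved minus control.
- The same with unresolved = 1, controls 0: b3 is resolved minus control.
- The same with resolved = 1 and controls also 1: controls change by b2 + c, resolved by b2 + b3 + c. So b3 is resolved minus control.
- R centred within the OSAS group, 0 in controls, times P: the average OSAS change is b2 + b3. So b3 is the total contrast, and c separates unresolved from resolved children.
- Extra term c·(AHI change)·P: b3 is the contrast at zero AHI change, that is, the effect not explained by AHI.

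**Illustrative size.** The documents give no resolution rate, AHI distribution, within-child correlation or recovery size. Assumed: 50 per group, 30% unresolved, correlation 0.6, visits at 0, 6 and 12 months, baseline deficit 0.566 SD, made up fully in resolved children and not at all in the others. The total contrast is then 0.70 × 0.566 = 0.396.

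| Coding | Expected b3 | Simulated mean |
|---|---|---|
| Neither term | 0.396 | 0.394 |
| Both as child-level main effects | 0.396 | 0.394 |
| Indicator × post, resolved = 1, controls 0 | 0 | -0.001 |
| Indicator × post, unresolved = 1, controls 0 | 0.566 | 0.564 |
| Indicator × post, resolved = 1, controls 1 | 0.566 | 0.563 |
| Centred indicator × post, controls 0 | 0.396 | 0.393 |
| AHI change × post | depends on AHI distribution | 0.262 |

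The controls = 1 and centred rows come from 1,500 simulated data sets, the others from 2,000.

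Power of the model with neither term, by hand: the variance of (mean of two follow-ups minus baseline) is (1 + 0.6)/2 + 1 - 2 × 0.6 = 0.6. Mixed recovery adds 0.30 × 0.70 × 0.566² = 0.067 in the OSAS group. SE = √(0.6/50 + 0.667/50) = 0.159. Then 0.396/0.159 = 2.49 and power ≈ Φ(2.49 - 1.96) = 70%, against 71% simulated.

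**Other recovery mechanisms, 30% unresolved.**

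- Recovery proportional to the absolute AHI fall: 0.394 with neither term, -0.001 with AHI change × post.
- Recovery proportional to the relative AHI fall: 0.372 and 0.258.
- Recovery unrelated to AHI: the estimate holds (0.394 and 0.395), but power falls from 73% to 54% with AHI change × post, and to 47% with both terms × post.

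A separate simulation with different AHI assumptions set a total effect of 0.20 + 0.03 × 10.68 = 0.52, of which 0.20 does not run through AHI. It gave 0.518 with neither term, 0.518 with both as main effects and 0.198 with both × post.

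**The case against.** The strongest defence is that 6.4.2 names only one interaction, time by group, and merely includes the other two terms. Read that way they are child-level main effects and the interaction is undisturbed. The complete-data condition also fits a plan that limits its primary analysis to children who complete all visits. This stands. A reader might infer that adjusting for results of surgery necessarily biases the treatment effect; the documents do not support that, because the zero-at-baseline coding it needs is nowhere stated. What the defence does not rescue is the indicator's purpose. As a main effect it adjusts only a child's overall level. That is a possible but weak sense of accounting for unresolved children.

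Three other strong readings also fail:

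- That no single model can do both jobs. The centred indicator crossed with time does; the plan simply does not state it.
- That coding resolved as 1 always yields the effect in unresolved children. It does so only with controls at 0.
- That power collapses to 6-8%. Where the true term is zero, that rejection rate is a false-positive rate, not power. Where the term is not zero but means something else, its power answers a different question.

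Sections 4.1.3 and 6.4.2 are also not a flat contradiction. A pooled model and a separate report on children with residual disease can coexist, but neither section says which is the main analysis.

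**Conclusion.** The concern holds as a fault of specification. The treatment-effect model has no fixed estimand: under codings that 6.4.2 leaves open, one coefficient can be the total contrast, the part not explained by AHI, or the contrast for one subgroup. The change of meaning follows from the algebra. The sizes (0.39, 0.00 and 0.56 in the all-or-none scenario) rest on the assumed resolution rate, correlation, AHI distribution and recovery mechanism, and are illustrations only. When recovery is unrelated to AHI, the cost is precision alone.

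The reach is limited. The GEE is described as exploratory and serves a secondary objective. The baseline OSAS-control comparison, which is the primary endpoint, and the sample size are not affected. The plan should be amended before analysis, but this does not undermine the study.

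**What to change.** 1. Main longitudinal GEE: group, time, group-by-time and baseline confounders only, keeping all operated children whatever their Visit 3 AHI. Describe the interaction as the difference in change over time between operated children with OSAS and controls who were not randomised. Calling it the average effect of surgery would claim too much.
2. Supplementary model: three-level group (control, resolved, residual OSAS at Visit 3) by time, or the equivalent centred indicator by time. State the definition of resolution and reconcile it with section 4.1.3. Label the model descriptive, because the groups are formed after surgery.
3. Use AHI change only in an OSAS-only model of its association with CBF change, which serves the severity endpoint in section 6.2, or in a model labelled as mediation.
4. State that the separate analysis in section 4.1.3 is supplementary to the pooled model.

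The cost is SAP wording and one extra model, with no new data. The resolved-only estimate is somewhat less precise than the pooled one. Under the same assumptions its SE is 0.160 against 0.156 with 15% unresolved, 0.168 against 0.157 with 30%, and 0.185 against 0.158 with 50% (about 3%, 7% and 17% larger). The main model will no longer show how much of the effect runs through AHI; that question moves to the model in item 3.
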